4. STUDY OBJECTIVES

4.1 Primary Objective

Specific Aim 1: To conduct a prospective open label proof-of-concept clinical trial in 50 patients with Type II diabetes evaluating the effects of MRA + Patiromer on LV mass and plaque regression over 12 months of treatment by MRI. Primary outcome measures will be change in LV mass of patients receiving Patiromer + Spironolactone at the end of 12 months and end-point of safety during this period. An additional co-primary measure will include percent change in atheroma volume (PAV) in the thoracic aorta on Patiromer + Spironolactone at the end of 12 months. Additional secondary measures will include central aortic blood pressure, 24-hour mean systolic blood pressure and measures of insulin resistance (HOMA-IR) at 12 weeks.

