where N_{group} is the number of patients in the group. **PAV or % change in total atheroma volume= Primary end-point**

To account for possible different median number of slices $N_{median-group}$ of the two groups, the normalized total plaque volume change in Spiro and placebo will be additionally calculated as: $Normalized \Delta TPV_{group} = \Delta TPV_{group} \times \frac{N_{median-group}}{N_{median-opposite-group}}$.

Secondary End-points: Patients will undergo 24-hour ABP and Central Aortic Blood pressures using a validated device (Oscar 2™system from SunTech Medical®), measuring BP at 15-minute intervals during the day (07.00 h–22.00 h) and at 30-minute intervals during the night (22.00 h–07.00 h), was used to measure ABPM. Aldosterone and HOMA-IR measurements after overnight fast after resting for 30 minutes after arrival and prior to IV placement and/or MR assessment. Fasting (9 hour) basal insulin sensitivity will be measured by the validated HOMA-IR index. $HOMA-IR = \text{insulin } (\mu\text{U/mL}) \times \text{glucose } (\text{mmol/L}) / 22.5$ (77). 24-hour ABP will be performed at visit 2 and visit 6.

6.2 Aim 2 Monocyte and Inflammation Studies: Peripheral blood mononuclear cells (PBMC) will be isolated via and purified with anti-human CD14 mAb immobilized on magnetic beads using the MACS system (Miltenyi Biotec) and purity confirmed by flow cytometry. Isolated cells will be lysed for RNA purification (see below). A portion of the PBMCs will be frozen at -80°C in RPMI medium with 20% FBS and 10% DMSO (1x10⁷cells/vial) for concurrent future flow analysis. This protocol has been shown to not affect future analysis of surface marker staining (78). We have considerable experience performing flow analysis in batched frozen monocytes to enhance reproducibility. Multicolor flow cytometry analysis will be performed using Anti-human CD14, CD16, CD206, and CD163 antibodies (BD Biosciences). Analysis will initially enumerate the quantity of CD14^{hi}CD16^{lo}, CD14^{hi}CD16^{hi} and CD14^{lo}CD16^{hi} monocytes which are similar to what has been described (79). The CD14^{hi}CD16^{hi} and CD14^{lo}CD16^{hi} monocytes are believed to represent inflammatory monocytes in the human. Isolated mRNA will be analyzed for classic inflammatory genes (M1) M2 markers (alternate activation) as well as candidate miRs.

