7.2 Inclusion Criteria

1. Male or female patients > 45 or > 40 years with known atherosclerotic events (examples include MI, Stroke) and able to provide informed consent (females must be either post-menopausal for one year, surgically sterile, or using effective contraception. Oral contraceptives are disallowed).
2. Patients with type II diabetes with HbA1c ≤ 9.0 on stable anti-glycemic regimen

that may include oral and/or injectable therapy (GLP-1/Insulin etc.). Changes in dose of glycemic regimen is allowed during the course of the trial if felt to be clinically appropriate.
3. GFR <70 and evidence of proteinuria (Urine Albumin/Creatinine Ratio of >30 mg/g or equivalent) in a urine specimen within 12 months OR GFR <60 mg/g regardless of proteinuria
4. Patients must be on ACE and/or ARB therapy with no planned dose adjustments.
5. Serum K ⁺ ≥ 4.6 meq/L at visit 0 (screening).

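### HOMA-IR change is confounded in patients on injected insulin, and the plan has no analysis rule for insulin users or for glycemic dose changes

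*Combined protocol and SAP*

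**What the plan says.** Section 4.1 lists among the secondary measures "measures of insulin resistance (HOMA-IR) at 12 weeks". Section 6.1 (Secondary End-points) sets the method: after a 9-hour fast, basal "insulin sensitivity will be measured by the validated HOMA-IR index", with the formula insulin (µU/mL) × glucose (mmol/L) / 22.5. The sampling conditions are "Aldosterone and HOMA-IR measurements after overnight fast after resting for 30 minutes after arrival" and before line placement or imaging. The section does not name an insulin assay, does not record when insulin was last injected, and does not restrict the index by treatment.

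Inclusion criterion 2 in Section 7.2 requires "Patients with type II diabetes with HbA1c ≤ 9.0 on stable anti-glycemic regimen" and continues "that may include oral and/or injectable therapy (GLP-1/Insulin etc.). Changes in dose of glycemic regimen is allowed during the course of the trial". Section 8 asks for medication to stay unchanged where medically possible, and then repeats the allowance for glycemic dose changes. No exclusion criterion in Section 7.3 removes insulin users. Section 9.3.2 states that there is no control product.

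Section 15 gives only two-sided tests, a log transformation for most continuous measures, and the promise of a detailed SAP. Section 11.2 lists no C-peptide; the carboxyl-terminal peptide there is a collagen marker.

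**The concern.** HOMA-IR is the product of two quantities, and insulin treatment acts on both. Injected insulin can enter the insulin term directly, and it lowers the glucose term. In an insulin user the result therefore reflects the patient's own secretion, the injected product and its glucose-lowering effect together. If the dose changes between the samples, the index changes for a reason unrelated to spironolactone or patiromer.

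A randomised comparison could remove much of this, because background dose changes would occur in both arms. Here every patient receives the study drugs, so there is nothing to subtract. A spurious fall would be easy to accept as real, because Section 2.1 presents improved insulin resistance as an expected effect of mineralocorticoid receptor antagonism. A spurious rise could hide a real benefit.

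**Working it through.** The documents give no effect size, SD, power or expected share of insulin users for HOMA-IR, so there is no planned figure to reproduce. The check applies the protocol's formula to assumed values and then asks what reaches the group result.

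**Step 1. One patient.** Formula (Section 6.1): HOMA-IR = insulin × glucose / 22.5. All insulin and glucose values below are assumptions.

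| Case | Insulin | Glucose | HOMA-IR | Change |
|---|---|---|---|---|
| Baseline | 15 | 8 | 15 × 8 / 22.5 = 5.33 | – |
| Assay detects 10 more, glucose unchanged | 25 | 8 | 8.89 | +67% |
| Assay detects 10 more, glucose falls | 25 | 7 | 7.78 | +46% |
| Assay does not detect the product; own insulin and glucose fall | 12 | 7 | 3.73 | -30% |
| As above, larger fall | 10 | 6.5 | 2.89 | -46% |

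If the detected addition ranges from 5 to 40 µU/mL and follow-up glucose from 8 to 6.5 mmol/L, the change runs from +8% to +267%. No case includes an effect of study drug. The sign depends on whether the assay detects the injected product and on how far glucose falls. The documents settle neither.

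**Step 2. The group.** On the log scale of Section 15, let a share f of patients have a dose change that multiplies their index by r, with no change in the others. The spurious change in the geometric mean is exp(f × ln r) − 1.

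- r = 7.78 / 5.33 = 1.46: f = 10% gives +4%, and f = 60% gives +25%.
- r = 2.89 / 5.33 = 0.54: f = 10% gives -6%, and f = 60% gives -31%.

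The range of f is assumed. The log transformation turns a multiplicative error into a shift of the mean; it does not remove it.

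**Step 3. Precision after restriction.** Let g be the share on injected insulin at baseline, with the full 50 of Section 9.1 and the same SD of the log change in those kept. The interval widens by about 1/√(1 − g).

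- g = 10%: 45 patients remain, 1/√0.9 = 1.05.
- g = 30%: 35 remain, 1/√0.7 = 1.20.
- g = 60%: 20 remain, 1/√0.4 = 1.58.

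**Step 4. Time available for dose changes.** Section 4.1 says 12 weeks. The HOMA-IR row of the schedule in Section 11.1 has two marks, apparently at Visits 2 and 8, although the table is broken in the text. Those visits are headed weeks 5 and 53, and 53 − 5 = 48 weeks. How long regimen changes can accumulate depends on which statement governs.

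**The case against.** The strongest reply is that the plan contains no wrong analysis. It defers the analyses to a SAP, requires a stable regimen at entry, asks for unchanged medication where possible, and schedules a medication log and repeated HbA1c. It allows changes in dose and does not expressly allow starting insulin. All of this is true and limits the problem. It does not remove it: stability is required at entry only, the same criterion then permits changes, and no rule says how the logged data will be used.

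A reader might infer that the index measures the injected drug instead of insulin resistance, or that doubling injected insulin doubles the index. The documents support neither. The formula shows only that the index scales with measured insulin. Whether measured insulin includes the injected product depends on the product, the assay and the time since injection, none of which is given. The doubling example also holds glucose fixed, although glucose is the other factor and the treatment is given to lower it.

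A reader might also infer a stated rule that HOMA-IR is analysed in every patient, or that every dose change will be read as a drug effect. Neither is written. The first is an inference from the lack of any restriction; the second depends on an analysis not yet specified.

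Finally, one could object that restricting the analysis to patients off insulin at both samples would itself bias it: patients who worsened and started insulin would drop out, with no control arm to reveal this. That objection stands, and the fix below is built around it.

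**Conclusion.** The point holds as a gap in the analysis plan for one secondary measure. HOMA-IR has no rule for insulin users or for glycemic dose changes. In insulin users its change is confounded, in a direction and by an amount that the documents do not determine. Without a control arm, a dose change between samples cannot be told apart from a study-drug effect.

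The sizes in the working illustrate what is possible; they do not estimate what will happen. They rest on assumed insulin and glucose values and an assumed share of affected patients. No primary outcome depends on this measure. It should still be settled before analysis, because the remedy is cheap and uses data already scheduled.

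**What to change.** Write the following into the SAP before the data are analysed:

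1. **Main analysis.** Analyse HOMA-IR change in patients not on injected insulin at the baseline measurement. Membership is then fixed before follow-up, and patients who start insulin later stay in.
2. **Insulin users at baseline.** Report them separately, with glucose and HbA1c, and do not interpret their HOMA-IR as insulin resistance.
3. **Sensitivity analysis.** Use the medication log to exclude patients who started insulin or changed their glucose-lowering regimen between the two samples. Label this as conditioning on a post-baseline event, and report how many patients it removes.
4. **Time point.** Reconcile the 12 weeks in Section 4.1 with the schedule in Section 11.1, and name the two visits that define the change.

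The cost is SAP wording and a smaller sample for this one measure, with the loss of precision shown in the working. The absolute number may be lower still: the COVID-19 plan in Section 11.3 closed enrolment permanently, with three sites having enrolled nobody, and the number enrolled is not given. No new data collection and no change to patient care are needed.

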6.3 Safety Evaluations

- Change in clinical laboratory findings (e.g. BUN, Creatinine, electrolytes).
- Incidence of adverse events

7. SUBJECT SELECTION

7.1 Study Population

Subjects with a diagnosis of Type II Diabetes who meet the inclusion and exclusion criteria will be eligible for participation in this study. Labs drawn within 3 months of the screening visit may be used to determine eligibility.

7.2 Inclusion Criteria

1. Male or female patients > 45 or > 40 years with known atherosclerotic events (examples include MI, Stroke) and able to provide informed consent (females must be either post-menopausal for one year, surgically sterile, or using effective contraception. Oral contraceptives are disallowed).
2. Patients with type II diabetes with HbA1c ≤ 9.0 on stable anti-glycemic regimen

that may include oral and/or injectable therapy (GLP-1/Insulin etc.). Changes in dose of glycemic regimen is allowed during the course of the trial if felt to be clinically appropriate.
3. GFR <70 and evidence of proteinuria (Urine Albumin/Creatinine Ratio of >30 mg/g or equivalent) in a urine specimen within 12 months OR GFR <60 mg/g regardless of proteinuria
4. Patients must be on ACE and/or ARB therapy with no planned dose adjustments.
5. Serum K ⁺ ≥ 4.6 meq/L at visit 0 (screening).

7.3 Exclusion Criteria

1. Uncontrolled hypertension (SBP>160 and/or DBP>95 mmHg at visit 0 (screening) and SBP >145 mm Hg at visit 2).
2. GFR (MDRD) of <15 at visit 0 (screening)
3. K ⁺ <4.6 meq/L at visit 0 (screening).
4. LDL cholesterol >150 mg/dL
5. Plasma triglycerides > 400 mg/dl
6. Contraindications to MRI (metallic implants, severe claustrophobia).
7. Acute coronary syndrome, Transient ischemic attack, CVA or critical limb ischemia during the last 6 months or coronary/peripheral revascularization within the last 3 months .
8. Evidence of a secondary form of hypertension.
9. Initiation of new therapy with statins, ACEI/ARB, antioxidants, CCBs, diuretics, β blockers.
10. Type I diabetes mellitus
11. Known contraindication, including history of allergy to Spironolactone or Patiromer
12. Any surgical or medical condition which might alter pharmacokinetics of drug (e.g. renal transplant, liver failure, liver transplant)
13. Concurrent potentially life threatening arrhythmia or symptomatic arrhythmia.
14. Significant hyponatremia defined as Na <130 meq/L.
15. History of prior malignancy including leukemia and lymphoma (but not basal cell skin cancer, cured squamous cell cancer and cured prostate cancer).
16. History of any severe, life-threatening disease.
17. Any surgical or medical conditions which place the patient at higher risk derived from his/her participation into the study, or likely to prevent patient from complying with requirements.
18. History of drug abuse within the last 2 years, noncompliance and unwillingness/inability to consent.
19. Pregnant women and nursing mothers
20. Class III or IV Congestive Heart Failure
21. Primary Hyperaldosteronism

7.4 Recruitment Strategy

All patients will be carefully evaluated for study eligibility during screening and will be recruited from clinics at University Hospitals' healthcare systems. The medical records

will be accessed to determine eligibility. PHI will be accessed during the pre-screening portion for medical review. A full waiver is requested. The 2 -week run-in-phase- period will permit assessment of patient compliance as well as determination of baseline sitting blood pressures. Patients must have met all inclusion/exclusion criteria before starting any parts of the study phase. We may call patients who have expressed interest in the study, using an approved phone script. No cold calling will be done. The phone script will be used for patients who would like to be contacted regarding more information about the study after their physician has given them some initial background in person or by letter.

Patients will also be recruited from referrals of the private practice of [name].

7.5 Multi-Site Research

MAGMA Add On is a multi-site study that includes NYU Winthrop, University of Maryland, and MetroHealth Systems. NYU Winthrop and the University of Maryland are responsible for their own local IRB while UH will be the IRB of record for MetroHealth System.

In addition to University Hospital CMC recruited patients, UH clinical staff including, DCRU nurses, clinical coordinators, radiology technicians, and PI(s) will also be responsible for assisting Visit 2 & 8 for Metro Health. A research coordinator from Metro Health will be primarily in charge of the coordination of the visit which includes escorting the patient, documentation, and record keeping.

8.1 Prohibited Medications and Treatments

The following medications are prohibited during the study:

Oral contraceptives

9 STUDY TREATMENTS

9.1 Method of Assigning Subjects to Treatment Groups

Up to 50 eligible patients will participate in the study. All study participants will undergo a two week run-in period with Patiromer. Then study medication will be commenced at 12.5 mg Spironolactone and Patiromer 8.4 g/d and escalate to 25 mg Spironolactone over

4 weeks. If needed, to manage K⁺, Patiromer will increase to 16.8 g/d. Then the treatment phase will commence with tolerated dose of Spironolactone along with Patiromer for 48 weeks.

9.2 Blinding

This research protocol is not blinded.

9.3 Formulation of Test and Control Products

9.3.1 Formulation of Test Product

Spironolactone is an antihypertensive potassium sparing diuretic and Mineralocorticoid (Aldosterone) Receptor Antagonist.

Patiromer (Veltassa) is a potassium binder indicated for the treatment of hyperkalemia.

9.3.2 Formulation of Control Product

There is no control product in this research protocol.

9.3.3 Dosage

If screening K 4.6-5.2; start Spironolactone “run-in phase” 25 mg qd x 1 week; at 1 week recheck K and creatinine and add Veltassa 8.4 mg qd and continue with the treatment phase

If screening K 5.3-5.5 start Spironolactone 12.5 mg and Veltassa 8.4 mg without a run-in phase and follow the Spironolactone dose escalate phase as in current protocol followed by the treatment phase

If screening K >5.5 start Veltassa “run-in phase” 8.4 mg qd x 2 weeks and Add Spironolactone after 2 weeks 12.5 mg qd with plan to dose escalate to 25 mg qd as per current protocol

The dose may need to be adjusted during the study due to safety lab results (e.g. K⁺) or if BP <100 mmHg. The study physician will adjust dose as needed.

The active ingredient is patiomer sorbitex calcium, which consists of the active moiety, patiromer, a non-absorbed potassium-binding polymer, and a calcium-sorbitol counterion. Each gram of patiromer is equivalent to a nominal amount of 2 grams of patiromer sorbitex calcium. Therefore, patients will be dosed at 8.4g of patiromer = 16.8g of patiromer sorbitex calcium (one packet) at the start of the study, increasing to 16.8g of patiromer = 33.6g of patiromer sorbitex calcium (two packets) as needed, according to the potassium levels during the study.

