6. CRITERIA FOR EVALUATION

6.1 Aim 1A Protocol

[figure not shown]
Cardiac and aortic MRI images will be obtained at Visit 2 and Visit 8. Patients will be imaged on a 3T 32-channel whole-body MR imaging system (Trio 3.0T, Siemens, Erlangen) with maximum gradient amplitude of 60 mT/m and a slew rate of 400 mT/m/ms. The system's integrated body coil will be used for radiofrequency signal transmission. Signal reception will be accomplished with the use of two flexible 6-element phase array body coil matrix in combination with the spine coil. After acquiring the low resolution, images for localization, each patient will undergo trueFISP cine imaging (8–10 short axis and 3 LV long axis with 20–30 cardiac phases depending on heart rate). Additional details on sequence parameters are provided on the Manual of operations. Following acquisition of cardiac MRI images, fat suppressed 3D turbo-spin echo (TSE) images using, dark blood acquisition protocol, based on SPACE sequence with 1mm³ resolution. MRI parameters are as follows: TR/TE= R-R interval/22ms, field of view FOV=320x272 mm², slices per slab 56, averages =1.7, bandwidth-BW=781Hz/px, echo spacing=2.9ms, turbo factor= 45, echo train/slice=3.

Quantitative evaluation:

LV mass estimation: the images from the participating sites will be loaded onto a dedicated workstation (*Leonardo*TM, Siemens Medical Solutions, Erlangen, Germany). Using specialized software (*Argus*TM, Siemens Medical Solutions, Erlangen, Germany), the short-axis views of the heart will be automatically sorted into slice positions (rows)

and cardiac phases (columns). End-diastole (ED) and end-systole (ES) will be visually identified as those phases with maximum and minimum area in a midventricular short-axis view of the LV cavity, using the position of the mitral and aortic valve as an aid to identify the phase of the cardiac cycle. The images will be cropped and zoomed to enhance detection of the myocardium-blood pool and myocardium-fat interfaces.

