11.1 Schedule of Events

11.1.1 Main Study Phase

TABLE 4	SCREEN		RUN-IN PHASE		DOSE ESCALATE				TREATMENT PHASE							
					M2	M2	M 2		M 3	M 5	M 7	M 9	M 11	M 12	M 13	
MONTH*	M1		M1		W5	W6	W8	W9	W11	W17	W25	W33	W41	W45	W53	
WEEK	W 1	W2	W3	W 4												
VISIT NUMBER	0		1		2	3	4	5	6	TF1	7	TF2	TF3	TF4	8	
Screening Labs (Renal function panel, Lipid panel, HbA1C, Urine sample Alb/Creat)	X															
Safety Labs (Renal function panel) Mag level*					X*	X	X	Optional	X*		X					X*
History & Targeted Assessment			X								X					X
EKG			X													
Vital Signs or 24-hour BP SphygoCor cuff * (includes central aortic BP))	X		X		X*		X		X*		X					X
Phone Call										X		X	X	X		
MRI					X				X							X
Research Labs/Monocyte Studies, (including PIP, PIINP, CITP and chemokines CCL2, CX3, CL1, and CCL5)					X				X							X
Insulin/Glucose (HOMA-IR)					X											X
HbA1C					X						X					X
Plasma Renin/Aldosterone					X											X
Medication Log		X				X			X	X	X	X	X	X	X	X
Pill counts					X				X		X					X
Dietary survey/instructions		X														X
Urine sample (Albumin/Creat)		X			X				X		X					X
Spot Urine Na/K/Creat					X											
Interim Event log					X		X		X	X	X	X	X	X	X	X
Questionnaire & Instructions			X													

A complete medical history and physical exam will be performed at baseline and will include a 12-lead electrocardiogram (EKG), cardiovascular risk factor assessment, intercurrent CV events, 7-day physical activity recall, active/passive smoking questionnaires and dietary recall questionnaire. Sitting systolic blood pressure, pulse rate, body weight, interim event logs, pill counts, medication logs will be recorded at most clinic visits. Central aortic blood pressure and pulse wave velocity will be obtained during

visit 2 (base), 6 (mid-point) and 8 (exit) while 24-hour BP will be measured at Visit 2 and 6.

Dietary Na⁺ consumption: Since Na intake is an important determinant of MR responsiveness we will ensure that all patients receive dietary survey/instructions (Visit 0) on maintaining a personalized diabetic diet that is stable and is medium to low in sodium (<4 g). We will obtain Na, K and Creatinine levels (Visit 1) to assess Na intake. The kawasaki formula will be used to estimate 24 hour urine.

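### Sections 9.1 and 9.3.3 conflict on the starting regimen for screening K 4.6-5.5, and for K 4.6-5.2 the Visit 2 baseline most naturally falls after about one week of spironolactone

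*Combined protocol and SAP*

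**What the plan says.** Section 9.1 describes one regimen for everyone: "All study participants will undergo a two week run-in period with Patiromer". It continues: "Then study medication will be commenced at 12.5 mg Spironolactone and Patiromer 8.4 g/d", with spironolactone rising to 25 mg over four weeks.

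Section 9.3.3 describes three regimens, chosen by screening potassium:

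- **K 4.6-5.2:** spironolactone 25 mg alone for one week, labelled a run-in, then "at 1 week recheck K and creatinine and add Veltassa 8.4 mg qd and continue with the treatment phase".
- **K 5.3-5.5:** both drugs together, spironolactone at 12.5 mg, "without a run-in phase and follow the Spironolactone dose escalate phase as in current protocol followed by the treatment phase".
- **K above 5.5:** two weeks of patiromer, then spironolactone 12.5 mg with a planned rise to 25 mg.

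(The milligram unit for patiromer in 9.3.3 is a separate slip; grams are used elsewhere.)

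Several measurements hang on Visit 2. Section 6.1 says "Cardiac and aortic MRI images will be obtained at Visit 2 and Visit 8". Section 11.1.1 places central aortic BP at "visit 2 (base), 6 (mid-point) and 8 (exit) while 24-hour BP will be measured at Visit 2 and 6". Section 7.3 excludes patients with uncontrolled pressure at screening "and SBP >145 mm Hg at visit 2". Section 7.4 still describes a two-week run-in and says this "run-in-phase- period will permit assessment of patient compliance as well as determination of baseline sitting blood pressures". It also requires eligibility to be settled before the study phase begins, without defining that phase.

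Section 9.3.2 states that there is no control product. Section 15 says a detailed SAP will be written before the final analysis.

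**The concern.** Only the K above 5.5 path in 9.3.3 agrees with 9.1. The inclusion criteria admit K from 4.6 upwards, so the two conflicting paths cover eligible patients, and no section says which text governs.

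This matters because, without a control arm, change from Visit 2 is the efficacy estimate. Section 9.3.1 describes spironolactone as antihypertensive. If some patients have their baseline BP taken on it, part of the drug's effect already sits in the baseline, and the measured fall to Visit 6 tends to be too small. The Visit 2 systolic limit would also be easier to pass in that stratum. A pooled 6-week change would then mix different contrasts: adding patiromer to spironolactone in K 4.6-5.2, starting both drugs in K 5.3-5.5, and adding spironolactone to patiromer in K above 5.5.

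**Working it through.** **Inputs.** From Table 4 in section 11.1.1, as far as the extracted layout can be read: run-in in W3-W4, Visit 2 at W5 (opening dose escalation), Visit 3 at W6, Visit 6 at W11, Visit 8 at W53. Regimens are from 9.1 and 9.3.3.

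**Check on the plan's own intervals.** Visit 2 to Visit 6 is 11 - 5 = 6 weeks, matching the 6-week BP time point in sections 2, 3 and 5. Visit 2 to Visit 8 is 53 - 5 = 48 weeks, the length 9.1 gives for the treatment phase. Visit 2 is therefore the baseline for both changes.

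**Regimens side by side.**

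| Screening K | Section 9.1 | Section 9.3.3 | Drug before Visit 2 under 9.3.3, most natural reading |
|---|---|---|---|
| 4.6-5.2 | Patiromer 2 weeks, then both drugs, spironolactone 12.5 to 25 mg | Spironolactone 25 mg alone 1 week, then patiromer added; no escalation step | Spironolactone, about 1 week |
| 5.3-5.5 | Same | Both drugs together, no run-in, then escalation | None |
| Above 5.5 | Same | Patiromer 2 weeks, then spironolactone 12.5 to 25 mg | Patiromer only, 2 weeks |

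The last column follows from three points. In K 4.6-5.2, 9.3.3 calls the spironolactone week a run-in, and Table 4 puts the run-in before Visit 2; the one-week potassium recheck fits the Visit 2 safety labs. In K 5.3-5.5 there is no run-in, so the first dose most naturally falls at Visit 2. In K above 5.5 the two run-in weeks are patiromer alone.

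**Exposure share in K 4.6-5.2.** Share = weeks on spironolactone before Visit 2 / (those weeks + weeks from Visit 2).

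- Visit 6: 1 / (1 + 6) = 1/7 = 14.3%.
- Visit 8: 1 / (1 + 48) = 1/49 = 2.0%.
- If BP were read at 12 weeks, as section 4.1 says: 1 / (1 + 12) = 1/13 = 7.7%.

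**Time on both drugs at Visit 8.** On this reading it runs from W5 to W53, 48 weeks, in all three strata. Treatment length does not differ; only the baseline does.

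**From exposure to effect (illustration only).** Let q be the share of patients with an on-spironolactone baseline and f the fraction of the BP effect already present at Visit 2. If the true effect is the same in all patients and the other baselines carry none of it, the pooled measured change is (1 - q x f) of the true change. The documents give neither value. For assumed q of 0.3 to 0.7:

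- f = 1/7 (effect proportional to time): shortfall 0.3/7 = 4.3% to 0.7/7 = 10.0%.
- f = 0.25 to 0.75: shortfall 0.3 x 0.25 = 7.5% to 0.7 x 0.75 = 52.5%.

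The width of that range shows that the documents do not settle the size.

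**The case against.** The strongest reply is that sections 7.3 and 7.4, read together, do anchor Visit 2: systolic pressure at Visit 2 is an exclusion criterion, and all criteria must be met before the study phase. A reader might infer that nothing at all links Visit 2 to dosing, and that goes too far. The anchor is still incomplete. The study phase is undefined, and even 9.1's uniform regimen gives patiromer in a run-in that Table 4 places before the Visit 2 check, so the phrase cannot mean before any study drug.

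A second reply is that K 4.6-5.2 patients may have started spironolactone at Visit 2, with the one-week recheck at Visit 3 (W6). Their baseline would then be drug-free. This is possible, but fits less well with 9.3.3 calling that week a run-in. That path also skips dose escalation, the block Visit 2 opens, so applying Table 4's weeks to it is an assumption.

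Three stronger inferences are tempting and not supported:

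- **Two weeks of prior spironolactone in K 4.6-5.2**, giving 2/8 = 25% at Visit 6. The text specifies one week.
- **The same problem in K 5.3-5.5.** It would need dosing during run-in weeks that 9.3.3 says this stratum does not have.
- **Reading 14% as the share of BP effect lost.** That needs effect to accrue in proportion to time, for which the documents give no basis. The loss could be larger or smaller.

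It is also fair to say that the consequence is limited. BP is a secondary measure and the likely bias runs against the treatment. Enrolment is permanently closed, so the point bears on interpretation and not on future dosing.

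**Conclusion.** The conflict between 9.1 and 9.3.3 for K 4.6-5.5 is plain on the text. Its main statistical consequence is narrower: following 9.3.3 as written, the K 4.6-5.2 baseline most naturally comes after about one week of spironolactone 25 mg. That would tend to understate the uncontrolled BP change from Visit 2 to Visit 6 and should matter little for LV mass and percent change in atheroma volume (PAV) over 48 weeks.

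This is a minor point, held with medium confidence. It assumes that Table 4's weeks, read from a damaged table, apply to every path and that the site followed 9.3.3. Enrolment by stratum is not given, so the number of patients affected is unknown. For any patient measured before first dose the concern disappears. A reader might infer that the LV mass or PAV results are compromised; a 2% exposure share gives no support for that.

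**What to change.** In the SAP:

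1. Record the regimen each enrolled patient actually received.
2. Classify each Visit 2 baseline as no drug, patiromer only, or spironolactone with or without patiromer, using diary dates (section 9.5) and dispensing records (section 9.4). Note any recent pre-study MRA use as well: section 5 admits patients whose potassium rose on an MRA, and no washout is stated, so study-drug dates alone could label a recently treated patient as unexposed.
3. Report the BP changes, and the LV mass and PAV changes, with and without patients whose baseline followed spironolactone. State that including them would tend to understate the BP change.
4. State which BP time point applies, since section 4.1 (12 weeks) disagrees with the 6 weeks given elsewhere.

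Correct sections 9.1 and 7.4 and Table 4 to match the regimen actually used. Declaring now that 9.3.3 governs could misdescribe what was given if the site followed 9.1.

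The cost is a text correction, a few sentences in a document not yet written, and the drug start dates and Visit 2 date for each patient, from records the protocol already requires, plus a note of prior MRA use. No extra patients, visits or tests are needed. The drawback is that the estimate in the smaller set is descriptive and less precise.
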